1.3 SCHEDULE OF ACTIVITIES

Schedule of interventions and of monitoring patient outcomes		Week of Study			
Outcome	Measure	1	2	3	4
Primary	Engagement: usage days, technique/sessions completed, log-ins, coach contacts				X
	Self-efficacy (SCSES)	X			X
	Mental Health Stigma/ SCD stigma	X			X
Process Evaluation	Perceived relevance and relatability			X	
	Depression (PHQ-9), Anxiety (GAD-7)	X	X	X	X
Quality of Life	Pain interference (PROMIS)	X			X
	Quality of life (ASCQ-Me)	X			X
Medical	Health care utilization: Opioid prescriptions, ED visits, hospitalizations				X

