2.3.3 ASSESSMENT OF POTENTIAL RISKS AND BENEFITS

While enrolled in the study participants will be given access to a health coach. Health coaches are trained personnel in dealing with individuals at risk, and are skilled at working with individuals at risk of feeling anxious or depressed. They will frequently assess participant risk and act accordingly.

Patients are able to stop the digital CBT program at any time, and we will frequently remind patients that they do not have to answer questions if it makes them uncomfortable.

Data Security

Coded data will be stored electronically and saved onto a separate secure database. Once the participant consents, the encrypted data is sent to a RedCap (or similar) secure server. There are two parts to the encrypted data that is transferred from the mobile device to the server: identifiable information upon enrollment and the non-identifiable study data. These two components are stored separately and linked by a unique identifier. The key linking these two are only accessible by the study staff.

This study involves the collection of data over the Internet using mobile devices. Although every reasonable effort will be taken, confidentiality during Internet communication procedures cannot be guaranteed and it is possible that additional information beyond that collected for research purposes may be captured and used by others not associated with this study

Patients will be encouraged to lock their device when not in use and to keep the latest security OS update. Patients will also be encouraged to avoid accessing untrusted sites.

This research is necessary to understand the feasibility of a mobile-technology-based behavioral intervention for mental health that predominantly targets a minority population.

Study endpoints

Primary Outcome Measures

Program engagement. Engagement will be measured by frequency and time on the app, number of lessons completed, and number of interactions (app messages) with health coaches over a 4-week period.

Secondary Outcome Measures

Pain Interference. The PROMIS Pain Interference Scale[86] is a validated questionnaire asking a patient how much day-to-day function is altered by pain. SCD impairs health-related quality of life (HR-QOL) more than most other chronic diseases. PROMIS is designed to allow streamlined, computer-aided administration, and has been tested in multiple populations and conditions including SCD.

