8 STATISTICAL CONSIDERATIONS

8.1 SAMPLE SIZE DETERMINATION

We anticipate randomizing, in an equal allocation ratio, a total of 40 participants with follow-up through at least 4 weeks, which will be the main time point for primary analysis.

For the primary test of engagement comparing standard vs. adapted digital CBT, the power calculation is based on the comparison of intervention groups for the main outcome of difference in usage days modules completed. Based on prior data (see preliminary data - Digital CBT in Medical Clinics), we would expect 50% less engagement for African Americans vs whites with our standard digital CBT app. Thus, to detect a 150% improvement in engagement related to adapted vs standard CBT for usage days (e.g 20 vs 10 usage days), with 80% power, a total of N=34 (n=17 per arm) is necessary. We are accounting for 10% attrition at 4 weeks.

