8.3.2 ANALYSIS OF THE PRIMARY AND SECONDARY ENDPOINT(S)

Primary and Secondary Analyses. We will employ linear regression models for the primary outcome of usage days and the secondary outcome of techniques and sessions completed (Hypothesis 1) as a function of study arm (standard CBT vs. adapted CBT). We will account for multiple observations for each participant by including a random effect for subject. Additionally, baseline variables with clinically meaningful between-arm differences will be included as covariates.

Process evaluation. Change scores, baseline to 4 weeks, perceived stigma, relevance, relatability, will be tested as potential mediating variables. Contrasts will be estimated to assess the impact of standard and adapted CBT intervention on 4-week differences in perceived relevance, relatability, and stigma. We will then test whether lower perceived mental health

stigma and higher perceived program representativeness and relevance in the adapted CBT arm, mediates any observed group differences in engagement and program satisfaction.

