8.3.5 ADDRESSING MISSING DATA

We will minimize missing data by use of a paperless data collection system and by contacting participants when data are not entered in a timely fashion. We will attempt to characterize the mechanism of missingness (missing completely at random, missing at random, or not missing at random) by comparing rates of missingness/attrition between study arms. Additionally, we will compare baseline characteristics between participants with and without missing outcome data. If we conclude that our missingness is random, then our likelihood-based approach for the primary analyses will address this. Otherwise, if the missingness can be characterized as non-ignorable (not missing at random), we will use approaches such as joint modeling or shared parameter models to produce unbiased estimates of treatment effects. All reasons for dropout or other missing values will be entered by research staff or community groups (if encountering the patient during community activities), tabulated and summarized, and results will be reported using the Consolidated Standards of Reporting Trials (CONSORT) diagram. Patients who stop reporting data in the app will receive inquiry text messages or a phone call.

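### If usage days is one 4-week total, the likelihood remedy in 8.3.5 is a complete-case regression that need not include baseline variables found to predict missingness

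*Combined protocol and SAP*

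**What the plan says.** Section 8.3.2 gives the primary model: "We will employ linear regression models for the primary outcome of usage days", as a function of arm. It then adds a random effect for subject to handle repeated observations per person, and a covariate rule: "baseline variables with clinically meaningful between-arm differences will be included as covariates".

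Section 8.3.5 sets out the handling of missing data. To judge the mechanism, attrition is compared between arms and "we will compare baseline characteristics between participants with and without missing outcome data". If missingness is judged random, "If we conclude that our missingness is random, then our likelihood-based approach for the primary analyses will address this". If it is judged non-ignorable, "we will use approaches such as joint modeling or shared parameter models to produce unbiased estimates of treatment effects". Section 8.3.6 mentions propensity score methods for missing data as a possibility, without naming variables or a model.

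On the shape of the outcome, the schedule in 1.3 lists "Engagement: usage days, technique/sessions completed, log-ins, coach contacts" with a single mark, at week 4. The endpoint text under 2.3.3 defines engagement by app use, lessons and "number of interactions (app messages) with health coaches over a 4-week period". Section 8.1 sizes the trial on one count per person (20 vs 10 usage days) at 4 weeks and states: "We are accounting for 10% attrition at 4 weeks".

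**The concern.** A likelihood analysis has an advantage over complete cases when a participant with missing values still contributes some outcome data, or when the model contains the variables that explain the loss. With one total per participant the first condition is absent, and the plan does not secure the second. The check in 8.3.5 may show that, say, participants with higher baseline depression more often lack outcome data. Nothing then carries that variable into the model unless it also happens to differ between arms, and yet the plan treats the problem as handled.

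The size of the arm difference in usage days is at stake. The trial hypothesises that engagement differs by arm, so loss that works differently in the two arms is plausible.

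**Working it through.** **The plan's own figure.** Section 8.1 gives 17 per arm, 80% power and 20 vs 10 days. It states no SD, alpha or sidedness, so N=34 can only be solved backwards. With two-sided 5% (assumed):

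- Normal approximation: SD = 10 / [√(2/17) × (1.960 + 0.842)] = 10.4.
- t-test: standardised difference 0.991, so SD = 10/0.991 = 10.09.
- Attrition: 34/0.90 = 37.8, so 38 are needed. With 40 randomised, 10% loss is 4 people and 36 remain.

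**One value or several?** The schedule, the endpoint text and 8.1 all fit a single 4-week total. The model for usage in 8.3.2 has no time term, whereas the PHQ-9 model in 8.3.9 has time and time-by-arm. Only the random subject effect in 8.3.2 points to repeated usage data, and no repeated usage outcome is defined. One total is therefore the better-supported reading, but it remains an inference.

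**What the likelihood does with one row per person.** The model is y ~ Normal(b0 + b1·arm, σu² + σe²). Only the sum of the two variances enters. In a simulated data set of 36 people, the log-likelihood was −131.508 at intraclass correlations of 0, 0.25, 0.5 and 0.9 alike. The random effect is not identified, a participant without a total contributes nothing, and the fit is complete-case regression.

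**Bias when a predictor of loss is left out.** Let x be a standardised baseline variable with correlation ρ to usage, with the same treatment effect at every x. Then

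bias = SD × ρ × (mean of x among those observed, adapted arm − the same, standard arm).

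This is zero when selection on x is the same in both arms. Large-sample simulation used assumed values: SD 10, true difference 10 days, ρ 0.3–0.5, and a logistic slope of 1.5 for loss on x, so that people with low x are lost more often in the standard arm. The loss rate was the same in both arms. Bias in days with x omitted:

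| Loss | x acts alike in both arms | x acts in one arm only | x acts in opposite directions |
|---|---|---|---|
| 10% | about 0 | −0.4 to −0.6 | −0.7 to −1.2 |
| 25% | about 0 | −0.9 to −1.4 | −1.6 to −2.7 |

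With x in the model the bias was about zero in every cell.

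**Trial-sized version.** Assume 20 per arm, SD 10.09, ρ 0.3–0.5, slopes 1–2, and the planned 10% loss falling wholly in the standard arm (20% vs 0%). The bias was roughly −0.6 to −1.4 days (a repeat run gave −0.5 to −1.3), with 95% interval coverage of about 93% to 95%. The standard error with 16 and 20 completers is 10.09 × √(1/16 + 1/20) = 3.4 days, so the bias is 0.6/3.4 to 1.4/3.4, or about 0.2 to 0.4 standard errors.

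**If usage were four weekly values.** With 35% of participants incomplete and dropout depending on earlier weeks, the mixed model was essentially unbiased (+0.02 days) while complete cases were off by −4.3 days. The choice between total and weekly counts therefore decides whether the sentence in 8.3.5 is true.

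**The non-ignorable branch.** With a single total there are no repeated outcome values to identify a shared random effect. The estimate then rests on an assumed distribution that the data cannot test.

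**Bounds.** A 4-week total lies between 0 and 28 days. One missing total can move an arm mean of 20 people by at most 28/20 = 1.4 days. Four missing totals give an unadjusted range of at most 4 × 1.4 = 5.6 days, and less once days already logged are counted.

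**The case against.** The strongest reply is that 8.3.2 describes a mixed model with repeated observations. If usage is modelled week by week, the likelihood approach does use partial data, and the simulation above agrees. This stands as a reason to state the point conditionally. It does not remove it, because no weekly usage outcome is defined.

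A reader might infer that both remedies in 8.3.5 simply fail. The documents do not support that:

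- Complete-case regression is valid if loss depends only on arm and on included covariates.
- A predictor of loss does enter the model if it is also imbalanced between arms.
- The list of non-ignorable methods is open-ended, and the weekly PHQ-9 and GAD-7 could feed a joint model, although none is specified.
- Section 8.3.6 leaves propensity methods available as an option.

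A reader might also infer that four primary outcomes will be missing. Usage is app activity, whereas 7.3 defines missed follow-up by uncompleted questionnaires. A participant who leaves the app or skips surveys may still have a known, low count, so four is towards the upper end if attrition is 10%.

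Finally, the bias is small beside the standard error, and interval coverage stays close to nominal. In the scenarios shown it understates the adapted arm's benefit, although the sign would reverse if the selection ran the other way. All of this limits the weight of the point. It does not supply the missing rule that links the check on missingness to the model.

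**Conclusion.** The point holds conditionally and is modest in size. If usage days is one total per participant, the remedy for random missingness is complete-case regression, and no rule brings baseline predictors of missingness into it. The resulting bias is about zero when loss acts alike in both arms, and roughly 0.4 to 1.4 of 10 days when a predictor acts in one arm only at 10–25% loss. It is larger only if the predictor acts in opposite directions. These figures rest on assumed SD, correlation, slope and loss pattern, since the documents give none of them. The claim of unbiased estimates in the second branch is not justified for a single total. Sections 1.3 and 8.1 need to be reconciled with the random subject effect in 8.3.2. The change is worth making because it costs almost nothing.

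**What to change.** 1. In 8.3.2, state whether usage days is analysed as one 4-week total or as weekly counts, and align the random-effect sentence with that choice. Define when usage is missing. Count app-recorded use for participants who stop using the app or skip surveys, so that only totals that are truly unavailable are missing.
2. Include baseline PHQ-9, baseline GAD-7 and recruitment source (clinical or community) in the primary model, fixed in advance and regardless of imbalance between arms.
3. In 8.3.5, replace the promise attached to joint and shared-parameter models with a pre-specified bounds analysis. Set each missing total between the days already logged and the maximum still possible, low in one arm and high in the other and then reversed, and report the range of the arm difference.

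Cost: SAP wording and a few lines of code, with no new data and no more participants. With recruitment source as two categories, the three covariates use 3 degrees of freedom (36 − 2 = 34 residual becomes 36 − 5 = 31). The reported range may be wide, at most 5.6 days if four totals are missing. Adjustment removes only the bias carried by the included variables, and the bounds cover the rest.

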8.3.6 SUB-GROUP ANALYSES

Planned sensitivity analyses to determine the impact of key assumptions. The major assumption is that patients will complete the intervention program to which they are randomly assigned. Although we have implemented several methods to promote engagement and limit dropout (e.g., health coaches[94]), digital interventions often experience high attrition over time with few participants completing all assigned modules.[95] We will track the reasons for non-completion and seek patterns (e.g., moved away, died, started working and became too busy, people with higher cognitive level lost interest) that are amenable to statistical analysis of the missing data. Sensitivity to this assumption can be determined by comparing analysis by three levels of participation in the intervention: enrollment and intervention assignment (Intent-to-Treat), participation in at least half the intervention, and zero participation in the intervention. Propensity score methods could also be used to deal with missing data. We will also test for differences in retention by recruitment site (e.g., community vs. clinical).

The comparative effectiveness trial with two active arms might show that both interventions work moderately well, which means there might not be superiority for the entire population. One intervention might be more suitable for certain subgroups of patients, so our Aim 2 analysis of primary and secondary outcomes by mental health subgroup should provide valuable information on suitability of the intervention for different subgroups.

8.3.9 EXPLORATORY ANALYSES

Due to limited power, evaluation of secondary outcomes will only be exploratory. Linear mixed models will account for change in outcomes over time. Depression (PHQ-9) will be modeled as a function of time, study arm, and time-by-study arm interaction. We will account for multiple

observations for participant by including a random effect for subject. As a secondary investigation, we will test group differences in pain intensity using a similar strategy.

Medical record review will be performed at 12 months post participation. Healthcare utilization will be compared between study arms using generalized linear models to account for count data (i.e., Poisson regression) for each of the following: the number of opioid prescriptions, number of ED visits, and number of hospitalizations over 12 months post study entry. Predictors will include study arm, study site, and baseline depression level. The corresponding health care utilization in 12 months prior to study entry will be entered as a covariate in each model. We will offset each model by participant's time on the study.

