All participants will complete short surveys each week they are in the study. These surveys will be sent to their mobile phone as a web URL link. Each week, participants will complete a depression (PHQ-9) and anxiety (GAD7) symptoms questionnaire. At 1 and 4 weeks only, participants will also complete measures of Self-efficacy (SCSES), stigma, pain interference (PROMIS), and quality of life (ASCO-ME). In addition, as part of the intervention, participants are asked to interact with their assigned digital CBT program at least once per week if not more.

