6.1.2 ADMINISTRATION AND/OR DOSING

For at least 4 weeks, participants will engage in one of two CBT programs administered through a digital mobile app. Participants will be asked to interact with their assigned program at least once per week, if not more. Both programs will provide participants with brief 5-10 minute skill building modules. In addition to the app-delivered content, participants will also receive weekly (more frequent if requested or needed) follow-up with a health coach. Health coach sessions will reinforce CBT content and encourage participant completion of modules for at least 4 weeks.

All participants will complete short surveys each week they are in the study. These surveys will be sent to their mobile phone as a web URL link. Each week, participants will complete a depression (PHQ-9) and anxiety (GAD7) symptoms questionnaire. At 1 and 4 weeks only, participants will also complete measures of Self-efficacy (SCSES), stigma, pain interference (PROMIS), and quality of life (ASCQ-ME).

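### For pain interference and quality of life, measured only twice, the stated mixed model amounts to a change-score comparison; adjusting for baseline would be more precise and needs no new data

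*Combined protocol and SAP*

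**What the plan says.** The synopsis (section 1.1) names pain interference and quality of life as the secondary endpoints. The schedule (section 1.3) places both at weeks 1 and 4, and sections 4.1, 6.1.2 and 7.3 agree: "At 1 and 4 weeks only, participants will also complete measures of" self-efficacy, stigma, pain interference and quality of life. The Study endpoints text after section 2.3.3 calls the first quality-of-life assessment the baseline.

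The analysis is in section 8.3.9: "Linear mixed models will account for change in outcomes over time". The only model written out is for depression: "Depression (PHQ-9) will be modeled as a function of time, study arm, and time-by-study arm interaction", with repeated measurements handled for the "observations for participant by including a random effect for subject". PHQ-9 is a weekly measure: "Each week, participants will complete a depression (PHQ-9) and anxiety (GAD7) symptoms questionnaire". For pain the plan adds: "As a secondary investigation, we will test group differences in pain intensity using a similar strategy". No model is written out for ASCQ-Me.

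The baseline value of the outcome is not named as a covariate for any questionnaire outcome. Section 8.3.2 brings in only those baseline variables that turn out to differ between arms. For the process evaluation it says: "Change scores, baseline to 4 weeks, perceived stigma, relevance, relatability, will be tested as potential mediating variables". By contrast, the health-care utilization models in section 8.3.9 do adjust for the same quantity in the 12 months before entry.

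**The concern.** With two occasions, a model with free arm means at both times and a time-by-arm term compares changes between arms. That comparison is valid under randomization, but it subtracts the whole baseline value, whereas the data support subtracting only the part that predicts week 4. The excess enters as noise. Section 8.3.9 already calls the secondary outcomes exploratory because power is limited, and a stated objective is to judge the feasibility of a larger trial. The estimates should therefore be as precise as the data allow. The plan adjusts for the prior value in the utilization models and gives no reason for not doing so here.

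**Working it through.** **Inputs**
- Occasions: baseline/week 1 and week 4 (sections 1.3, 4.1, 6.1.2).
- Completers: 40 randomized 1:1 with 10% attrition (section 8.1), so 40 × 0.90 = 36, or 18 per arm.
- Power 80% (section 8.1, stated for the primary outcome).
- Assumed, because not in the documents: the correlation r (shown from 0.3 to 0.8), equal SDs at both occasions, and two-sided 5% significance.

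**The plan's own figure.** The plan gives no precision, correlation or power figure for these outcomes. Its only calculation, N = 34 for usage days, states no SD or significance level and so cannot be reproduced independently. At two-sided 5%, 17 per arm and a 10-day difference imply an SD of 10/(2.8016 × √(2/17)) = 10.4 days. 34/0.90 = 37.8, or 38, which 40 covers. None of this bears on the twice-measured outcomes.

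**Step 1: what the model estimates.** With two occasions and complete data, the time-by-arm coefficient is (adapted week 4 − adapted baseline) − (standard week 4 − standard baseline), in means. This is the difference in mean change. Fitting the model to simulated two-occasion data gave an interaction of −0.4931 and a difference in mean change of −0.4931; two further data sets agreed in the same way.

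**Step 2: variance per participant.**
- Change score: 2σ²(1 − r).
- Adjusted for baseline: σ²(1 − r²).
- Ratio of adjusted to change: (1 + r)/2. Precision lost: (1 − r)/2.

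Equal SDs are not needed for the direction. With SDs σ₁ and σ₂, the change-score variance exceeds the adjusted one by (σ₁ − rσ₂)², which is never negative.

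**Step 3: numbers.** The standard-error column is 1 − √ratio. The simulated column is the variance loss from 20,000 simulated trials at each r with 18 per arm; it includes the cost of estimating the baseline slope. The detectable difference is 2.8016 × √(V × 2/18) in SD units, where V is the variance in column 2 or 3.

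| r | Change V | Adjusted V | Ratio | Loss, large sample | Loss in SE | Loss, simulated | Detectable difference, change vs adjusted |
|---|---|---|---|---|---|---|---|
| 0.3 | 1.40 | 0.91 | 0.65 | 35% | 19% | 32% | 1.105 vs 0.891 |
| 0.5 | 1.00 | 0.75 | 0.75 | 25% | 13% | 22% | 0.934 vs 0.809 |
| 0.7 | 0.60 | 0.51 | 0.85 | 15% | 8% | not run | 0.723 vs 0.667 |
| 0.8 | 0.40 | 0.36 | 0.90 | 10% | 5% | 7% | 0.591 vs 0.560 |

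The simulated variances (change, adjusted) were 0.155 and 0.105 at r = 0.3, 0.112 and 0.087 at r = 0.5, and 0.0455 and 0.0423 at r = 0.8.

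**Step 4: in participants.** At r = 0.5, the adjusted analysis of 36 completers is worth a change-score analysis of 36/0.75 = 48 by the large-sample formula, or 36/0.78 ≈ 46 with the simulated loss.

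**The case against.** The strongest objection is that the plan does not clearly prescribe this analysis. The model is written out only for PHQ-9, which is weekly, and extended by analogy to pain intensity, which is not in the schedule. The treatment contrast is never named. This stands in part. A reader might infer that the plan explicitly commits pain interference and ASCQ-Me to change scores. It does not; the model reaches them through the general sentence and the analogy. But it is the only strategy offered, and if it was not meant for them they have no stated analysis and need the same sentence.

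A complete-case analysis of covariance is not a free replacement when attrition is expected. A mixed model keeps a participant with one observation; analysis of covariance drops that person. This stands and shapes the fix.

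The value of adjustment depends on when baseline is taken. Section 5.5 links payment for the baseline assessment, among those randomized, with starting the program, and no section says that these measures precede allocation or app use. This also stands. A post-exposure first measurement would undermine adjustment, but it would equally undermine a change score, which would subtract part of any early effect.

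Stigma enters section 8.3.2 as a possible mediator, so the variance formula above does not measure any loss in the mediation test. That stands, and no figure is claimed for it.

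Finally, the outcomes are exploratory and the change-score estimate is unbiased under randomization. Both are true. Chance baseline imbalance is not a second harm; it is the source of the extra variance already counted.

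**Conclusion.** The point holds as a free improvement. For PROMIS pain interference and ASCQ-Me, the only stated model reduces to a comparison of change scores, and baseline adjustment estimates the same effect with less variance. If r lies between 0.8 and 0.3, the loss is 10% to 35% of precision in large samples, about 7% to 32% at 18 per arm, and about 5% to 19% in standard error by the large-sample formula. This rests on an assumed range of r, equal SDs at the two occasions, and a baseline taken before allocation or exposure.

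A reader might infer that a loss of 10% to 35% is a property of this trial. The documents give no correlation, so it is conditional, and it shrinks towards zero as r approaches 1. A reader might also infer that the trial's main comparison is weakened. It is not: the primary endpoint is engagement, and neither that analysis nor the sample size depends on this choice.

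**What to change.** In section 8.3.9, state for pain interference and ASCQ-Me that the treatment effect is the week-4 difference between arms adjusted for the participant's baseline value. The preferred form is a likelihood-based mixed model with baseline means constrained equal across arms (time and time-by-arm, no arm effect at baseline) and an unstructured covariance for the two occasions. Participants with one observation are then kept. With complete data, analysis of covariance gives essentially the same answer and can serve as a check.

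In the same revision:
- State that the baseline assessment is taken before allocation or app exposure. If it is not, neither the equal-means constraint nor the adjustment is justified as written.
- Name the pain measure consistently: the scheduled instrument measures interference, not intensity.
- In section 8.3.2, adjust the between-arm contrast in week-4 stigma for baseline stigma.
- Use screening PHQ-9 and GAD-7 as covariates only if both are recorded for every participant before allocation. Eligibility requires either scale above 4, so the documents do not show that both are held for all.

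The cost is wording in the analysis plan, with no new data or visits, provided that the baseline timing is confirmed.
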